1.2 Rationale

The deficiency in THR- β activity in NASH livers cannot be corrected by treatment with thyroid hormone because 1) thyroid hormone may be rapidly metabolized in NASH livers due to the action of deiodinases, and 2) thyroid hormone has undesirable systemic actions, particularly effects on the heart and bone because of its potency at the THR- α receptor.

Thyroid hormone receptor analogs demonstrating an improved therapeutic window between beneficial lipid effects and adverse systemic effects have been developed and tested in clinical trials and demonstrated validation of cholesterol and triglyceride lowering.^{14,15} However,

eprotirome and other analogs also demonstrated safety issues that resulted in discontinuation of clinical development. These include low margins relative to doses that suppress the central thyroid axis, elevated liver enzymes in Phase 1, 2, and 3 studies, and other safety issues such as formation of a nitrated mutagenic impurity at gastric pH and collagen damage in a preclinical toxicology study.^{16, 17}

The oral THR- β agonist MGL-3196 was selected for clinical development based on its enhanced THR- β selectivity in functional THR assays and its greatly improved safety in preclinical animal models relative to other THR analogues and T3.¹⁸ Unlike previous clinical analogues, MGL-3196 is highly THR- β selective in a functional coactivator recruitment assay and has virtually no THR- α activity. Liver uptake is mediated by hepatic transporters. In preclinical animal studies, MGL-3196 showed rapid and robust lowering of non-HDL cholesterol, triglycerides, and liver triglycerides, with reduction in NASH gene transcripts, differentiating MGL-3196 from statins and other lipid-lowering agents. In 14-day Phase 1 studies in healthy human volunteers, once-daily doses of MGL-3196 showed rapid, robust reduction of LDL-C and triglycerides. In these studies, there was apparent safety at all doses tested and no evidence of the liver enzyme changes or central thyroid axis suppression that were seen with T3, T4, or previous clinical thyroid analogues.¹⁹

2 STUDY OBJECTIVES

2.1 Primary Objective

The primary objective of this study is to determine the effect of once-daily oral MGL-3196 80 mg versus placebo (randomized 2:1) for 12 weeks on the percent change in hepatic fat fraction by proton density fat fraction magnetic resonance imaging (MRI-PDFF) from baseline in patients with biopsy-proven NASH.

2.2 Secondary Objectives

The secondary objectives of this study are the following:

- To determine the effect of once-daily oral MGL-3196 80 mg versus placebo for 36 weeks in patients with biopsy-proven NASH on the histological improvement from baseline on:
 - Two-point reduction in NAFLD activity score (NAS);
 - Resolution of NASH (ballooning = 0; inflammation = 0 to 1); or
 - Any individual component of NASH (hepatocellular steatosis, ballooning, fibrosis, or lobular inflammation);
- To evaluate the safety and tolerability, including any changes in thyroid axis hormones, of once-daily oral MGL-3196 80 mg versus placebo after 12 and 36 weeks in patients with biopsy-proven NASH;
- To evaluate the effect of once-daily oral MGL-3196 80 mg versus placebo for 36 weeks on the percent change in hepatic fat fraction by MRI-PDFF from baseline in patients with biopsy-proven NASH;
- To evaluate the effect of once-daily oral MGL-3196 80 mg versus placebo for 12 and 36 weeks on the change in hepatic fat fraction by MRI-PDFF from baseline in patients with biopsy-proven NASH; and
- To determine the effect of once-daily oral MGL-3196 80 mg versus placebo after 12 and 36 weeks in patients with biopsy-proven NASH on:
 - High-sensitivity C-reactive protein (hsCRP);
 - Serum alanine aminotransferase (ALT) and aspartate aminotransferase (AST);
 - Lipid parameters including LDL-C, HDL-C, non-HDL-C, total cholesterol, triglycerides, apolipoprotein B (ApoB), and lipoprotein(a) (Lp[a]) particles; and
 - NASH and fibrosis biomarkers including cytokeratin-18 (CK-18), fibrosis-4 (FIB-4), and enhanced liver function (ELF) test.

2.3 Exploratory Objectives

The tertiary/exploratory objectives of this study are the following:

This figure displays a 10x10 grid of black and white bars, representing a 2D convolutional feature map. The bars are arranged in a grid pattern, with varying widths and heights. The grid is composed of 10 horizontal rows and 10 vertical columns. The bars are black on a white background, and the grid is centered on a white background.

3 STUDY DESCRIPTION

3.1 Summary of Study Design

This is a multi-center, double-blind, randomized, placebo-controlled study to evaluate the safety and efficacy of MGL-3196 in patients with NASH. Patients who qualify for study inclusion will be randomized to receive one of two 36-week treatments: MGL-3196 80 mg or placebo given orally once-daily in the morning. Following 12 weeks of treatment, the primary endpoint, percent change from baseline in hepatic fat fraction measured by MRI-PDFF, will be evaluated. At 36 weeks, all patients will undergo liver biopsy.

3.1.1 Screening Period

Patients must provide written informed consent prior to any study procedures being performed. Patients will undergo screening procedures within 42 days of randomization. To participate in the study, patients are required to have had a qualifying liver biopsy within 180 days of randomization. Patients must meet all of the inclusion criteria and none of the exclusion criteria to participate in the study.

3.1.2 Treatment Period

Following randomization, patients will begin the initial 12-week Treatment Period. Patients will undergo liver MRI-PDFF prior to the start of treatment (pre-dose), at the end of the initial 12-week Treatment Period (12 weeks after the start of treatment), and after continuing blinded treatment (MGL-3196 or placebo) for an additional 24 weeks (36 weeks after the start of treatment). A liver biopsy will be obtained prior to start of treatment (pre-dose) if the patient has not had a qualifying liver biopsy within 180 days of randomization and at 36 weeks. During the study, patients will return to the study site periodically for assessment of vital signs (temperature, pulse, respiratory rate, and seated blood pressure), 12-lead electrocardiogram (ECG), and clinical laboratory testing (hematology, chemistry, and urinalysis). During the study, patients who need to be placed on any excluded lipid lowering therapeutics will be discontinued from the study. Blood samples will be collected at specified times for the assessment of lipid parameters, thyroid hormone parameters, and other biomarkers. Patients will be evaluated for adverse events and concomitant medication use throughout the study. Patients should be monitored throughout the study for clinical signs and symptoms of hyper- or hypothyroidism.

A PK assessment will be made at Week 2 including a pre-dose fasting determination and assessments at 2, 4, 6, and 8 hours postdose. As described in PK section, patients who have a calculated $AUC_{inf} \leq 5500 \text{ ng*hr/ml}$ (combined MGL-3196 and MGL-3196-M1) will continue on 80 mg. For patients (~ 10%) with an $AUC_{inf} \leq 3000 \text{ ng*hr/ml}$ as described in Section 8 who are predicted to have exposure at 100 mg that remains $AUC \leq 5550$ based on a conservative calculation, the MGL-3196 dose will be increased from 80 mg to 100 mg at the Week 4 visit. For patients with combined $AUC > 5500 \text{ ng*hr/ml}$, the dose of MGL-3196 will be reduced to 60 mg per day on the Week 4 visit. Patients with $AUC_{inf} > 11,000$ (combined MGL-3196 and M1) plus $SHBG > 150\%$ increase from baseline at Week 2 (indicative that average or steady-state exposure is $> 11,000 \text{ ng*hr/ml}$) will be downtitrated to 40 mg at Week 4. If $SHBG \leq 150\%$, then patient will be downtitrated to 60 mg at Week 4, and patient's Week 4 SHBG and predose concentrations will be evaluated. If at Week 4 $SHBG > 150\%$ increase from baseline and predose

>40ng/ml for MGL-3196 and >40ng/ml for M1 then patient will be downtitrated to 40 mg at the Week 8 visit.

A combined MGL-3196 and MGL-3196-M1 exposure \leq 5500 ng*hr/ml has not demonstrated a drug-related decrease in FT4 to $<$ LLN $<$ 0.7 ng/dL in Phase 1 studies. However, patients with NASH without symptoms of hypothyroidism may occasionally have low baseline levels of FT4, with normal FT3 and TSH, and are not clinically or subclinically hypothyroid. Low FT4 in the presence of normal FT3 (active hormone) and TSH is not consistent with hypothyroidism; low FT4 is observed in euthyroid (formerly hypothyroid) patients treated with T3 monotherapy²⁰

In patients continuing on 80 mg MGL-3196 (AUC_{inf} $<$ 5500) who have FT4 LLN ($>$.55 to $<$.7 ng/dL):

At Week 4 or later:

- If FT3 remains normal (not decreased to $<$ LLN) and TSH remains normal, the patient does not have symptoms of hypothyroidism, the patient may continue on the current dose.
- Down titration to 60 mg may be made at the next visit, Week 8 or later if FT4 $<$ LLN ($>$.55 to $<$.7 ng/dL), FT3 and TSH are normal, and there is evidence that the decrease in FT4 $<$ LLN ($>$.55 to $<$.7 ng/dL) is drug-related including a $>$ 30% decrease from baseline in FT4, an increase in SHBG $>$ 120% from baseline and predose exposure $>$ 40 ng/ml for MGL-3196 and $>$ 40 ng/ml for MGL-3196-M1 that is consistent with increased drug exposure relative to the Week 2 PK assessment.

In patients downtitrated to 60 mg at Week 4 who have FT4 LLN ($>$.55 to $<$.7 ng/dL):

- At Week 8 or later, if FT3 and TSH remain normal, the patient does not have symptoms of hypothyroidism, the patient may continue on the current dose.
- Down titration to 60 or 40 mg may be made at the next visit, Week 12 or later if FT4 $<$ LLN ($>$.55 to $<$.7 ng/dL), FT3 and TSH are normal, and there is evidence that the decrease in FT4 $<$ LLN ($>$.55 to $<$.7 ng/dL) is drug-related including a $>$ 30% decrease from baseline in FT4, an increase in SHBG $>$ 120% from baseline and predose exposure $>$ 40 ng/ml for MGL-3196 and $>$ 40 ng/ml for MGL-3196-M1 that is consistent with increased drug exposure relative to the Week 2 PK assessment.

If these conditions are not met, the patient will continue on current dose and thyroid indices reassessed at subsequent visits. Any randomized patients previously downtitrated based on LLN FT4 per Protocol Amendment 2 who did not meet these criteria for downtitration (Amendment 3) will be returned to the previous dose in a blinded fashion at the next visit.

If FT4 is \leq .55 ng/dL on 80 or 60 mg dose with normal FT3 and TSH (which are unblinded to study personnel for all patients), even if the decrease in FT4 is not felt to be primarily drug-related, a down titration to 60 or 40 mg, respectively, may be made at the next visit as determined by Sponsor and Medical Monitor after blinded review. If it is determined after blinded review by Sponsor and Medical Monitor that thyroid therapy should be initiated, because thyroxine cannot be initiated without breaking the blind, the patient will be discontinued from the study and Early Termination assessments will be performed.

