4.3 Withdrawal Criteria

Participation of a patient in this clinical study may be discontinued for any of the following reasons:

- The patient withdraws consent or requests discontinuation from the study for any reason;
- Occurrence of any medical condition or circumstance that exposes the patient to substantial risk and/or does not allow the patient to adhere to the requirements of the protocol;
- Any serious adverse event (SAE), clinically significant adverse event, severe laboratory abnormality, intercurrent illness, cardiovascular events such as new onset CHF, new onset or unstable angina or myocardial infarction, or other medical condition which indicates to the Investigator that continued participation is not in the best interest of the patient including

recurrent elevation of liver enzymes upon rechallenge or diagnosis of liver pathology other than NASH as described in Section 9.17;

- Pregnancy;
- Requirement of prohibited concomitant medication;
- Patient failure to comply with protocol requirements or study-related procedures; or
- Termination of the study by the Sponsor or the regulatory authority.

If a patient withdraws prematurely from the study due to the above criteria or any other reason, study staff should make every effort to complete the full panel of assessments scheduled for the End of Treatment Visit. The reason for patient withdrawal must be documented in the electronic Case Report Form (eCRF). In the case of patients lost to follow-up, attempts to contact the patient must be made and documented in the patient's medical records. Withdrawn patients will not be replaced.

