6.6 Early Termination Visit and Withdrawal Procedures

Patients who are withdrawn from either the **Main** Study or Extension Study prior to completion will return to the study site for the Early Termination Visit. The following Early Termination procedures will be completed:

Note: Completion of some procedures may depend on the guidance and discretion of the Investigators, Medical Monitors, and Sponsor taking into account factors such as why and when the patient terminated early.

- Perform 12-lead ECG;
- Perform symptom-directed physical examination;
- Assess study drug accountability;
- Collect vital signs and anthropometrics;
- Collect blood sample for:
 - Hematology profiles, fasting chemistry profiles, fasting metabolic panel, and fasting lipid parameters (see Appendix C for a full list of analytes to be measured);
 - Total and free (calculated) testosterone, LH, FSH, and estradiol;
 - CK-MB, troponin I, SHBG;
 - PK sampling (pre-dose);
 - ALP isoenzymes;
 - CK-18, FIB-4, and ELF;
 - Type 1 procollagen N-terminal propeptide and CTX;
 - Fibrinogen, haptoglobin, alpha-2 macroglobulin, proBNP, apolipoprotein C-III, and ferritin;
 - APTT, PT, INR;
 - hsCRP; and
 - Thyroid axis hormones;
 - Bile acid levels;

- Collect urine sample for pregnancy test (for women of child bearing potential only) and urinalysis;
- Perform liver biopsy (Main Study only);
- Perform DXA scan;
- Perform Fibroscan (if available);
- Complete HR-QoL SF-36 assessment;
- Perform MRI-PDFF; and
- Review alcohol consumption, concomitant medications, and adverse events.

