If close monitoring is not possible, study drug should be discontinued temporarily, pending further evaluation by the Investigator in collaboration with the Medical Monitor and Sponsor. If a patient lives in a remote area, they can be tested locally and the results communicated to the investigator site promptly.

Study drug must be temporarily discontinued if the above abnormalities are confirmed. Frequency of subsequent repeat assessments will be determined by Sponsor and Medical Monitor.

Study drug may be resumed once abnormal results return to the normal range or to the patient's baseline values.

Study drug must be permanently discontinued if any of the following criteria are met:

1. A definite new cardiovascular diagnosis is confirmed that is considered to be probably related to study drug.
2. Abnormalities in symptoms, ECG, or laboratory biomarkers recur following re-introduction of study drug.
3. Abnormalities in symptoms, ECG, or laboratory biomarkers do not return to normal or baseline values.

The required Early Termination Visit assessments will be performed (see Section 6.6).

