10.2 Statistical Methods

10.2.1 Analysis of Efficacy

10.2.1.1 Primary efficacy analysis

The primary efficacy variable will be the percent change in MRI-PDFF from baseline to Week 12. Summary statistics (number of patients, mean, standard deviation, median, minimum, and maximum) at all visits and change from baseline will be provided. The primary efficacy analysis will be analyzed with an analysis of covariance (ANCOVA) model with treatment as a factor. For any patients in the ITT Population with a missing primary efficacy parameter, the control (placebo)-based pattern mixture model will be used. Based on PK obtained in healthy volunteers dosed for up to two weeks on doses of MGL-3196 from 20-200 mg per day, a significant fraction of patients randomized to an 80 mg dose may have their dose reduced to 60 mg after PK assessment at Week 2. The multiplicity (MGL-3196 60 mg versus placebo and MGL-3196 80 mg versus placebo) will be controlled by Dunnett's Test. The primary efficacy analysis will be performed based on the ITT Population and repeated based on the Per Protocol Population.

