10.2.5 Sample Size Determination

Approximately 117 patients in total will be randomized to 80 mg (2/3) or placebo (1/3) treatments. After PK assessment, a significant fraction of patients' combined AUC (MGL-3196 plus MGL-3196-M1) may exceed 5500 ng*hr/ml resulting in a dose reduction to 60 mg. In order to power the study appropriately for an efficacious dose (which may be ≥ 80 mg), randomization may continue until approximately 36 patients have continued at Week 4 on the 80 mg dose. It is estimated that the treatment difference of percent change in hepatic fat fraction from baseline to Week 12 between any dose of MGL-3196 and the placebo group is about -30%. With a common standard deviation for the percent change in hepatic fat fraction at 35%, 36 patients per group completing the Week 12 visit will provide 90% power with a 2-sample t-test. The significance level is set as 0.025 for the consideration of multiplicity in comparisons of 2 daily dosing regimens

of MGL-3196 versus the placebo group. The enrollment size is designed to allow for 10% drop out before the Week 12 visit, and as such, patients who drop out of the study will not be replaced.

With the sample size of 39 patients per treatment, the power for selected secondary efficacy endpoints was calculated. The baseline hepatic fat fraction is expected to be approximately 15% to 17%, thus the change from baseline to Week 12 in hepatic fat fraction is approximately -5.5% when comparing to placebo. With common standard deviation of change in hepatic fat fraction as 6%, 36 completed patients will provide 94% power for the study when evaluating the treatment effect in change of hepatic fat fraction.

In addition, the sample size is expected to provide meaningful liver biopsy-related data.

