## **3. STATISTICAL METHODOLOGY**

### **3.1 Baseline, Endpoint, and Other Statistical Considerations**

Baseline for all efficacy and safety variables will be defined as Baseline visit (Day 1). If the measurement at this visit is missing, the last measurement prior to the first dose of randomized study drug will be used.

For efficacy variables other than hepatic fat fraction, early termination and unscheduled visits will be assigned a visit number based on the date of assessment relative to the first dose of the double-blind study drug. Visit windows will be defined as the scheduled time from dosing date with a 7-day window ( $\pm 7$  days). Within a visit window, if a scheduled visit occurs, then the measurement from this scheduled visit will be used as the measurement for this visit window. If no scheduled visit occurs within a visit window, the last measurement within the window will be used. If no visits occur within a visit window, the measurement of this visit will be treated as missing.

If the last dose date is missing due to subject lost to follow-up, then it will be assumed the subject is still on study drug at the last clinic visit. For lipids measurements, only data up to one day after the last dose will be considered valid and used in the analyses. For MRI-PDFF and liver biopsy results, the measurements up to three weeks after the last dose will still be considered valid and used in the analyses. For liver enzyme measurements, all the measurements will be used whether the subject is on or off study drug at the clinic visit.

If weight is missing at the Week 12 (or Week 36) visit and the subject completed the Week 12 (or Week 36) visit, the average of the weight at the previous scheduled visit and next scheduled visit will be used as the Week 12 (or Week 36) measurement.

Descriptive statistics (number of patients, mean, standard deviation, median, minimum, and maximum) will be used to summarize the continuous data. Discrete measures will be summarized using counts and percentages.

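### Several exits end study follow-up as well as study drug, and neither document then secures a usable Week 12 or Week 36 MRI-PDFF for the ITT analysis

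*Protocol*

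**What the plan says.** **Routes out of the study**

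- *Excluded lipid drug* (Synopsis and protocol 3.1.2), mandatory exit: "During the study, patients who need to be placed on any excluded lipid lowering therapeutics will be discontinued from the study".
- *Thyroxine* (3.1.2): if blinded review decides it is needed, the patient leaves and has Early Termination assessments. The note to Exclusion #5 in 4.2, and 5.6.1, instead let thyroxine be started during the study. These passages must be reconciled.
- *Permanent cardiovascular stop* (9.18) and *acute viral hepatitis* (9.17): Early Termination assessments follow.
- *Other prohibited medicines, failure to comply, adverse events* (4.3), permissive only: "Participation of a patient in this clinical study may be discontinued for any of the following reasons".

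**Assessments at exit**

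- Protocol 4.3: "study staff should make every effort to complete the full panel of assessments scheduled for the End of Treatment Visit". Neither Appendix A nor Appendix B has a visit of that name.
- Protocol 6.6 lists MRI-PDFF among the Early Termination procedures, but lets completion of some procedures depend on discretion, "taking into account factors such as why and when the patient terminated early". Appendix A, footnote 1, repeats this.

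**Analysis**

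- Protocol 10.2.1.1 makes ITT primary: "For any patients in the ITT Population with a missing primary efficacy parameter, the control (placebo)-based pattern mixture model will be used".
- SAP 3.7.2 analyses Week 12 fat fraction in the MRI-PDFF Evaluable population and gives no imputation. SAP 3.2.3 requires a baseline and a Week 12 scan.
- SAP 3.1 assigns early termination visits to visit windows for efficacy variables other than fat fraction, and accepts MRI-PDFF only up to three weeks after the last dose. For enzymes it is more open: "For liver enzyme measurements, all the measurements will be used whether the subject is on or off study drug at the clinic visit".

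**The concern.** An ITT analysis asks what happened to every treated patient, including those who stopped drug. For the exits listed above, the protocol stops looking, and no text in either document calls for the scheduled scan afterwards. A Week 12 or Week 36 outcome that could have been measured becomes either a model assumption or an exclusion.

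The exits need not be neutral. The Amendment 6 rationale reports that MGL-3196 lowered LDL-C, triglycerides and ApoB against placebo, so a need for excluded lipid drugs could lean towards placebo. Section 3.1.2 provides for drug-related falls in FT4, so thyroxine exits could lean towards active. Making the exit scan depend on the reason for leaving adds another way for missingness to follow outcome.

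**Working it through.** **1. Can the exit scan stand in for the Week 12 scan?** Take a patient who stops drug and leaves at Week 4. An exit scan taken then gets no Week 12 assignment, because SAP 3.1 leaves fat fraction out of its windowing rule, and the patient fails SAP 3.2.3. Suppose the patient were scanned at Week 12 instead: 12 - 4 = 8 weeks off drug, beyond the three-week limit in SAP 3.1. Either way, the SAP has no usable Week 12 value. For Week 36, SAP 3.7.2.5 offers an observed analysis and LOCF after Week 12. LOCF can use a later exit scan, but can also carry a Week 12 scan forward for someone who left afterwards.

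**2. How much was missing?** Counts are from the tables in the Amendment 6 rationale: treated 41 placebo and 84 active; both scans 38 and 78. One exposure-group table prints placebo N = 30, but 38 + 78 = 116 matches the text.

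- Placebo: (41 - 38)/41 = 3/41 = 7.3%
- Active: (84 - 78)/84 = 6/84 = 7.1%
- Overall: 9/125 = 7.2%, against a planned 10%
- Active minus placebo: -0.2 points (95% CI -12.9 to 8.8), Fisher p = 1.0. Reasons are not reported.

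**3. Effect on the SAP evaluable analysis.** With m_a and m_p the missing shares, and D_a and D_p the amounts by which missing patients differ from completers (positive is worse), all-patient difference = completer difference + m_a × D_a - m_p × D_p. The starting value of -30 is the assumed effect in protocol 10.2.5. D_a and D_p are my assumptions, given as a range.

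| Scenario | Observed rates | 10% per arm |
|---|---|---|
| D_a = 30, D_p = 0 | -30 + 2.14 = -27.9 | -30 + 3.0 = -27.0 |
| D_a = 30, D_p = -30 | -30 + 4.34 = -25.7 | -30 + 6.0 = -24.0 |
| D_a = 60, D_p = -30 | -30 + 6.48 = -23.5 | -30 + 9.0 = -21.0 |

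The first row, where active leavers lose the planned effect, is essentially what a placebo-based pattern mixture model assumes. The protocol's ITT analysis would largely absorb it. The other rows go beyond that model.

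**4. Power, before and after the change.** On alpha, protocol 10.2.5 says: "The significance level is set as 0.025 for the consideration of multiplicity in comparisons of 2 daily dosing regimens". It also gives a difference of 30, SD 35, 36 completers per group and 90% power. The noncentral t at two-sided 0.025 has noncentrality 30/(35 × sqrt(2/36)) = 3.64 on 70 df and gives 90.8%, which reproduces the 90%. One-sided 0.025 gives 94.8% and does not.

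Now suppose a share m of active patients stop drug, have placebo-like outcomes and are all scanned. The difference is 30(1 - m), and the active SD is sqrt(35² + m(1 - m) × 30²). At m = 10% these are 27.0 and sqrt(1225 + 81) = 36.1.

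| m | 39 v 39, all scanned, 0.025 | Completers only, 0.025 | 78 v 39 pooled, all scanned, 0.05 |
|---|---|---|---|
| 7.1% | 88.0% | 91.0% | 97.6% |
| 10% | 85.4% | 90.0% | 96.5% |
| 15% | 80.3% | 88.1% | 94.1% |
| 20% | 74.3% | 85.8% | 90.7% |

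**The case against.** The strongest reply is that the rule is narrower than it looks and the protocol already copes with it.

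- *Scope.* A reader might infer that any drug stop or poor compliance ends participation, making the ITT set resemble the per-protocol set. The documents do not support that. Protocol 5.5.4 answers compliance below 80% with counselling and exclusion from the Per Protocol Population only, and removal under 4.3 is permissive. After a liver-enzyme stop, 9.17 allows drug to be resumed. Cardiovascular stops are first temporary. SAP 3.2.5 lists not having stopped drug before Week 12 as a criterion within patients who already have a Week 12 scan, which presupposes that some stoppers are scanned. This objection stands and limits the point to the exits listed.
- *Arm link.* A reader might also infer that scans were lost unevenly. The counts show no imbalance. Lipid levels are blinded, allowed lipid therapies may be started (4.2, Exclusion #9), and 3.1.3 reports that FT4 downtitrations had not been needed. So the link is a risk only. Nine patients without stated reasons cannot exclude it, and exits in opposite directions could give similar counts. Some of the nine may have withdrawn consent or been lost, which no wording would change.
- *Mitigation.* The protocol's imputation largely covers the simplest scenario, and the 10% drop-out allowance already covers lost precision. Both are right for the protocol's analysis. SAP 3.7.2, however, does not carry the imputation over.
- *Exit scan.* MRI-PDFF is on the Early Termination list, and the visit name in 4.3 is probably a slip. True, but discretion and the SAP rules still leave no Week 12 value.
- *Power.* Retaining stoppers takes the 39 v 39 comparison below 90%. This is a real cost against the completer calculation. Placebo-based imputation dilutes the mean effect similarly in that scenario.

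**Conclusion.** The point holds in limited form. Need for an excluded lipid drug ends participation, as does need for thyroxine under 3.1.2. Certain permanent stops lead to Early Termination, and other removals are permitted. Neither document requires the scheduled scan afterwards, and the exit scan cannot replace the Week 12 value.

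The size is modest: about 2 points on a 30-point effect at the observed 7.1% in the active arm, and 3 points at the planned 10%. This assumes that missing active patients lose the whole effect, and it applies to the SAP's evaluable analysis. It is not a bias of that size in the protocol's ITT analysis. Nor do the documents show that any of the nine missing scans arose from these rules. The change is worth making because it is cheap and replaces assumed outcomes with observed ones in the analysis the protocol calls primary.

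**What to change.** Leave every drug-stopping rule as it is.

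**Protocol 3.1.2, 4.3, 6.6 and 9.18**
- State that stopping study drug or starting an excluded medicine does not by itself end study follow-up.
- Such patients keep their scheduled visits, and the MRI-PDFF already provided at exit is taken at the scheduled Week 12 or Week 36 date, flagged as off drug or after an excluded medicine.
- For patients who truly leave, do not make the exit scan discretionary by reason for leaving.
- Make the visit name in 4.3 match Appendices A and B.
- Reconcile the thyroxine passages in 3.1.2, 4.2 and 5.6.1, including the stated concern about breaking the blind.

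**SAP**
- In 3.7.2, add the protocol's ITT analysis of Week 12 percent change using the flagged scans, with the placebo-based pattern mixture model for values still missing.
- In 3.1, exempt that analysis from the three-week off-drug limit.
- Keep the 3.2.3 evaluable analysis as supportive, and say there that scans beyond the limit do not enter it.

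**Cost**
- Wording changes in both documents, and a few already-scheduled visits: for Week 12, about 12 patients at the planned rate (10% of 117 = 11.7). The scan is moved, not added.
- A somewhat smaller ITT effect: at 10% stopping with placebo-like outcomes, power is 85.4% for 39 v 39 at 0.025 and 96.5% for the pooled 78 v 39 contrast at 0.05.
- Week 12 had been read out by Amendment 6, so new collection helps only the remaining Week 36 follow-up. The Week 12 ITT analysis can still be added, since the protocol already specifies it.
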